11.0 RECRUITMENT

Approximately 8-12 study centres will participate in this study in order to enroll the number of participants outlined above. It is estimated that this study will take approximately 36 months to complete. This timeline is based on a 24-month participant recruitment timeframe and also assuming the collection of 8-week and 1-year follow-up data to examine the consequences of the GEN and E-GEN on patient outcomes, healthcare resource utilization and productivity losses. Changes to these assumptions will require

an adjustment of stated timelines. Participant recruitment plan details can be found in the study Project Management Plan.

12.0 METHODS: ASSIGNMENT OF INTERVENTIONS

12.1 Allocation

12.1.1 Sequence Generation

Participants will be randomly assigned to one of the three treatments arms with a 1:1:1 allocation as per a computer generated randomization schedule stratified by site using permuted blocks of random sizes. The block sizes will not be disclosed, to ensure concealment.

13.0 BLINDING

This study will be conducted under double-blind conditions so that neither the patient nor study staff members involved in patient assessments will know whether the patient is receiving GEN, E-GEN, or TAU. Only the treating clinician at the study site and AssureRx will have knowledge of the intervention arm assigned to the patient.

All assessments will be administered by the site, with the exception of the primary outcome measure (HAM-D₁₇), which will be conducted by 1-2 trained central rater(s) not involved in the clinical care of the individual and blinded to the treatment allocation. The rater will be trained and inter-rater reliability will be determined through rater scoring of the HAM-D₁₇ while viewing a DVD-recording of a standardized patient interview.

At randomization, the treating clinician will receive the results of the GEN test for patients allocated to GEN and the results of the E-GEN test for patients allocated to the E-GEN, and may decide to change the participant's treatment based on the results of the test. The treating clinician will therefore not be blinded to treatment allocation. AssureRx will also not be blinded to treatment allocation in order to release the appropriate report (either GEN, E-GEN or no report (TAU)) to the treating clinician and to provide follow-up support to the treating clinician on report interpretation. However, both treating clinician and AssureRx will be blinded to trial data.

14.0 METHODS: DATA COLLECTION, MANAGEMENT, AND ANALYSIS

14.1 Data Collection Methods

Data will be collected using a validated electronic data capture (EDC) solution. Electronic case report forms (eCRFs) will be utilized for recording data from each subject meeting the eligibility criteria and being randomized into the study. Electronic access to the CRF will be available to all Investigator sites. All study staff responsible for entering data into the eCRF system will be trained prior to the start-up of the study. A personal log-in will be provided for all responsible personnel to allow for an audit trail relating to the study data to be maintained.

All evaluations performed shall be entered in a timely manner into the eCRF by a member of the site staff delegated responsibility for this specific task by the Principal Investigator of the clinical site. It is the responsibility of the Investigator to ensure that the eCRFs are properly completed. The data in the eCRFs should be consistent with the relevant source documents. The Investigator will sign the designated signature fields of the eCRF to confirm that the information on each screen is accurate and complete. All data must be stored in an unidentifiable form treated with strict confidentiality in accordance with applicable data-protection regulations.

Captured data will be monitored electronically and source data verification (SDV) will take place at the site where all information will be verified against the individual patient records. Any inconsistencies will be presented as queries; either as automatically generated queries if raised by the logical data checks of the eCRF system, or by manually generated queries if raised by the data validation checks or the SDV performed by the data manager (DM) or the CRA respectively. Queries shall be resolved in a timely manner by a trained member of the site staff.

14.1.1 Participant Retention

Once a patient is enrolled, the study site will make every reasonable effort to follow the patient for the entire study period. If a patient fails to return for scheduled visits, a documented effort must be made to determine the reason. If the patient cannot be reached by telephone after two attempts, a certified letter should be sent to the patient requesting contact with the Investigator. This information should be recorded in the study records.

14.1.2 Participant Withdrawal

Early Withdrawal Criteria

Participants will only be withdrawn from the study for the following scenarios:

1. Participant withdraws consent for participation for any reason;
2. Participant is deemed lost to follow-up after all exhaustive measures have been taken to contact and locate the participant or the subject moves away;
3. A protocol violation occurs, whereby the respective Ethics Board or Sponsor requires that a participant is withdrawn from the study;
4. Participant dies;
5. A serious or life-threatening Reportable Event occurred or adverse event that prevents further participation;
6. Investigator judges that for any reason continuation of the study is inappropriate for the patient, this includes non-compliance with study procedures.
7. Participant permanently loses capacity to consent to research during participation in the study.

The reason for early withdrawal from the study will be documented, and all relevant CRFs will be completed. The Sponsor must be notified of all patient withdrawals as soon as possible.

If participant is withdrawn early, all efforts should be made to bring the patient in for an Early Termination (ET) visit as soon as possible (see section on Early Termination (ET) Visit).

If permission to use protected health information is withdrawn, it is the Investigator's responsibility to obtain a written request, to ensure that no further data will be collected from the patient and the patient will be removed from the study.

14.1.3 Discontinuation of Study

The Sponsor reserves the right to discontinue the study for any reason at any time and to discontinue participation by an individual Investigator or site for poor enrollment or noncompliance.

15.0 DATA MANAGEMENT

Data Management will be conducted by the sponsor appointed CRO.

Data will be transmitted electronically into the web based EDC system. Data will be coded according to pre-specified dictionaries and in accordance with the CRO Standard Operating Procedures (SOP). The handling of data, including data quality control, will comply with all applicable regulatory guidelines.

A detailed description of the analyses to be performed will be provided in the statistical analysis plan (SAP).

15.1 Inspection of Records

Monitors, auditors, and other authorized representatives of the Sponsor, the REB/IEC approving this study, Health Canada, other domestic government agencies, and other foreign regulatory agencies will be granted direct access to the study patient's original medical and study records for verification of the data and/or clinical trial procedures. Access to this information will be permitted to representatives of the aforementioned organizations to the extent permitted by law. The investigator(s) will be expected to cooperate with such a visit and to provide assistance and documentation (including all study documentation, and patient source data) as requested. Wherever possible de-identified data will be provided to protect participant privacy.

15.2 Retention of Records

The Investigator must maintain adequate and accurate records to enable the conduct of the study to be fully documented and the study data to be subsequently verified. These records include, but are not limited to, the identity of all participating patients, all original signed informed consent documents, copies of all CRFs, safety reporting forms, source documents, and detailed records of treatment disposition, and adequate documentation of relevant correspondence.

The Investigator shall retain study records for a period of 25 years or according to the institutional policy following the date a marketing application is approved for GEN or E-GEN for the indication for which it is being investigated; or, if no application is to be filed, or if the application is not approved for such indication, for a period of 25 years or according to the institutional policy after all investigations with the test are discontinued and Health Canada is notified.

If the Investigator moves, withdraws from an investigation, or retires, the responsibility for maintaining the records may be transferred to another person (e.g., Sponsor, other investigator) who will accept the responsibility. Notice of this transfer, must be made to the Sponsor.

16.0 STATISTICAL METHODS

16.1 Clinical Analysis

Hall-Flavin et al.(11) experienced significant participant attrition during the course of their investigation. Post hoc analyses using intention-to-treat (ITT) analyses, however, revealed little differences between the observed data and imputed data (e.g., last observation carried forward (LOCF) and estimation/maximization (EM) algorithm imputation). Two analyses will be completed with the study data: under the principle of intention-to-treat all randomized individuals will be analysed, i.e., the Full Analysis Set (FES), and a per protocol (PP) analysis for randomized participants where adherence to the protocol and visits was followed. Therefore, to account for participant attrition in the current study, ITT with multiple imputation with LOCF and EM algorithm imputation will be employed to account for missing data, assuming the data are missing completely at random. To assess the potential impact that the multiple imputation has on the final estimates, an EM algorithm imputation (iterative mean imputation) will be used as exploratory sensitivity analysis.

16.1.1 Descriptive Statistics

Continuous variables will be summarized with standard descriptive statistics including means, standard deviations, medians, and ranges. Categorical variables will be summarized with frequencies and percentages. Ninety-five percent confidence intervals will be provided for descriptive statistics, as warranted.

16.1.2 Diagnostics

Prior to formal statistical analyses, diagnostics will be conducted to determine appropriate statistical models. The independence assumption of ANOVA will be tested by examining the correlation between error terms for each dependent variable across levels of the indicator variable. To this end, the Durbin-Watson test statistic will be used to determine if the independence assumption was upheld. Values approaching 2.0 from the left or right were considered to be an indication of independence. The normality assumption will be tested by plotting residuals against the normal probability plot and by deriving the Shapiro-Wilk (S-W) test statistic. The dependent variable will formally be considered to be non-

normally distributed if the p-value for the S-W test was < 0.05 . Homogeneity of variance will be tested by employing the statistic derived by Brown and Forsythe. If the associated p-value for the test statistic is < 0.05 , then the dependent variable will be assumed to exhibit non-constant variance. If a given dependent variable did not meet the above mentioned assumptions (e.g., clustering due to study site), generalized estimating equations (GEEs) will be employed to account for the lack of independence between outcomes using an autoregressive correlation structure and identity link function.

16.1.3 Continuous Outcomes

If the HAM-D₁₇ scores from baseline to end of Week 8 of the study meet the assumptions of ANOVA modeling, repeated-measure (i.e., mixed) ANOVA models will be used to model the outcome scores over time. This model accounts for a between-group and within-individual effect, which allows for the examination of average differences between groups while also accounting for the correlation between participant scores between each measurement. If the HAM-D₁₇ scores do not meet standard ANOVA assumptions, GEEs will be used to model repeated measurements of outcome scores over time, as these models are more robust to departures from the standard assumptions and also allow the investigator to specify the correlation structure of the repeated measurements. Mean symptom improvement for all continuous measures (i.e., depression scales) will be calculated using the standard formula $(\frac{y_2 - y_1}{y_1}) * 100$, where y_1 is the baseline score for each participant for each rating scale and y_2 is the 8 week score for each participant for each rating scale.

Two hypotheses related to the primary objectives will be tested, where μ_1 is the mean HAM-D₁₇ % symptom improvement in the GEN group, μ_2 is the mean HAM-D₁₇ % symptom improvement in the E-GEN group and μ_3 is the mean HAM-D₁₇ % symptom improvement in the TAU group.

Primary objective (1):

$$H_0: \mu_1 = \mu_2 = \mu_3$$

$$H_a: \mu_1 = \mu_2 > \mu_3$$

Primary objective (2):

$$H_0: \mu_1 = \mu_2 = \mu_3$$

$$H_a: \mu_1 < \mu_2 > \mu_3$$

For all continuous measures, a responder will be defined as a participant with 50% change from baseline in total scale score. Remitters at week 8 and at week 12 will be defined as HAM-D₁₇ ≤7 in each treatment group. Differential time to response/remission of depressive symptoms over 8 and 12 weeks will be plotted using Kaplan-Meier curves and Cox proportional hazard models will test the null hypothesis of no difference in time to response/remission between groups.

16.1.4 Categorical Outcomes

Categorical outcomes (i.e., remission, response) will be analyzed with 2x2 contingency tables, logistic regression, or loglinear models, where appropriate. Relative risk of response and remission will be determined between each treatment arm (i.e., GEN and E-GEN) using the TAU group as the referent group and the standard formula $\frac{a/(a+b)}{c/(c+d)}$, where *a* is the number of responders/remitters in each GEN or E-GEN group, *b* is the number of non-responders/non-remitters in the GEN or E-GEN group, *c* is the number of responders/remitters in the TAU group, and *d* is the number of non-responders/non-remitters in the TAU group. Standard chi-square tests will be used to determine if the relative risk of response/remission is statistically significant between groups. If expected frequencies are too small for asymptotic assumptions, Fisher's exact tests will be employed to test for differences in categorical outcomes between groups. Ninety-five percent confidence intervals will be calculated and provided for the relative risk of response/remission between groups.

16.1.5 Within-Group and Between-Group Composite Phenotype Analyses

A three-level indicator variable (eg., green, yellow, and red categories) will be created using a proprietary algorithm which combines the phenotypes ascribed to each gene for each participant and drug metabolism information for each of the GeneSight panel drugs. This is done to reduce the dimensionality inherent to such data by generating a single composite phenotype for each participant. The final indicator variable will be labeled 'composite_phenotype,' with the first level scored as 'green,' (e.g., use medication(s) as directed) the second level scored as 'yellow,' (e.g., use medication(s) with caution) and the third level scored as 'red' (e.g., use medication(s) with caution and frequent monitoring). If parametric assumptions are upheld, 1-way independent ANOVA models will be employed to test the independent ability of the composite phenotype variable to predict each respective continuous outcome (i.e., percent improvement from baseline for HAMD-17) between study groups. If parametric (i.e., standard) assumptions are not met, GEEs will be employed to test the independent ability of the composite phenotype variable to predict each respective continuous outcome. Three tests will be conducted for each

continuous outcome: an overall ANOVA test and two planned contrasts involving the comparison of the first level (i.e., green category) to that of the third (i.e., red category), and the first two levels (i.e., green and yellow categories) of the composite phenotype variable to that of the third level. To account for multiple testing, the Sidak correction will be employed using the formula $1 - (1-\alpha)^{1/n}$ where n is the number of independent tests and α is the nominal level (i.e., 05) of statistical significance

16.1.6 Decision Rule

An overall alpha-level of 0.05 will be used to determine statistical significance and all statistical tests will be two-sided. All data will be analyzed using SAS (SAS Institute, Inc., Version 9.3, Cary, NC).

16.2 Economic Analysis

The economic analysis will include a detailed micro costing evaluation. Using the data collected from the trial and ICES as the foundation, this will be based upon both a 'within trial' analysis, as well as modeling and decision analytic techniques to estimate the long-term cost-effectiveness comparing the use of GEN, E-GEN and TAU. Analyses will be carried out from the perspective of the Canadian healthcare payer, but a societal perspective will also be considered (e.g. productivity costs due to absenteeism and disability).

17.0 METHODS: MONITORING

17.1 Data Monitoring

Monitoring visits will be conducted during the study at regular intervals. The monitoring visits will be conducted to ensure protocol adherence, quality of data, accuracy of entries in the eCRF, compliance with regulatory requirements and continued adequacy of the investigational site and its facilities.

Incorrect or missing entries in the CRFs will be queried and will be corrected appropriately.

All clinical data will undergo quality control checks prior to clinical database lock. Edit checks will then be performed for appropriate databases as a validation routine using SAS ® to check for missing data, data inconsistencies, data ranges, etc. Each eCRF is reviewed and signed by the principal investigator (PI).

17.2 Harms

The GEN and E-GEN is not a drug intervention, and this study is an evaluation of the impact of the results report on a patient's major depression.

Contact information for questions regarding GEN and E-GEN for this study is as follows:

Medical Information
Office [contact]
[contact]
Email: [contact]

17.2.1 Definitions

Adverse event (AE) means any untoward medical occurrence associated with the use of a drug in humans, whether or not considered drug related. An AE can therefore be any unfavorable and unintended sign (including a clinically significant abnormal laboratory finding), symptom or disease temporally associated with the use of an investigational product, whether or not considered related to the investigational product. Any worsening of a preexisting condition (i.e., any clinically significant adverse change in frequency and/or intensity) which is temporally associated with the use of the investigational product is also an AE.

17.2.2 Evaluating, Recording and Reporting of Adverse Events

At each visit all AEs that are observed, elicited by the Investigator, or reported by the participant, will be recorded in the appropriate section of the AE CRF and evaluated by the Investigator.

Minimum information required for each AE includes type of event, duration (start and end dates), severity, seriousness, causality to study drug, action taken, and outcome.

Severity of AEs will be graded by the Investigator using the following criteria as guidelines:

1. Mild: Nuisance, barely noticeable.
2. Moderate: Uncomfortable, troublesome symptoms not significantly interfering with daily activities or sleep.
3. Severe: Symptoms significantly interfere with daily activities or sleep.

The relationship of the AE to the study drug should be specified by the Investigator, using the following definitions:

1. Not Related: Concomitant illness, accident or event with no reasonable association with study drug.
2. Unlikely Related: The event has little or no temporal sequence from administration of the study drug, and/or a more likely alternative etiology exists.
3. Possibly Related: The event follows a reasonable temporal sequence from administration of study drug but which could also be explained by concurrent disease or other factors or medications
4. Probably Related: The event follows a reasonable temporal sequence from administration of study drug, unlikely to be attributed to concurrent disease or other factors or medications. A clinically reasonable response may be observed if the study drug is withdrawn or dose reduced.
5. Definitely Related: The event follows a reasonable temporal sequence from administration of study drug and is definitive pharmacologically; cannot to be attributed to concurrent disease or other factors or medications. A clinically reasonable response should be observed if the study drug is withdrawn or dose reduced.

If discernible at the time of completing an AE CRF, a specific disease or syndrome rather than individual associated signs and symptoms should be recorded on the AE CRF. However, if an observed or reported sign, symptom, or clinically significant laboratory anomaly is not considered by the Investigator to be a component of a specific disease or syndrome, then it should be recorded as a separate AE on the AE CRF (clinically significant laboratory abnormalities are those that are identified as such by the Investigator and/or those that require intervention).

Investigators should follow the Health Canada process for reporting untoward events of marketed medications by submitting a *Canada Vigilance Adverse Reaction Reporting Form* to MedEffect for a Serious Adverse Event (SAE):

A serious adverse event (SAE) is any untoward medical occurrence that at any dose (including overdose) that meets one or more of the following criteria:

- Is fatal, as a direct outcome of the AE

- Is life threatening
This serious criterion applies if the participant, in the view of the Investigator, is at substantial risk of dying from the AE as it occurs. It does not apply if an AE hypothetically might have caused death if it were more severe.
- Requires or prolongs inpatient hospitalization
This serious criterion applies if the reported AE necessitates an inpatient admission (in Canada) or a minimum 24-hour inpatient hospitalization (outside Canada) or, if in the opinion of the Investigator, prolongs an existing hospitalization. A hospitalization for an elective procedure, a routinely scheduled treatment or a social admission is not an SAE.
- Results in permanent or significant disability/incapacity
This serious criterion applies if the “disability” caused by the reported AE results in a substantial disruption of the participant’s ability to carry out normal life functions.
- Results in a congenital anomaly/birth defect
This serious criterion applies if a participant exposed to the investigational product gives birth to a child with congenital anomaly or birth defect.
- Requires intervention to prevent damage/permanent impairment
This serious criterion applies if the reported AE necessitates a medical or surgical intervention to preclude permanent impairment of a body function, or prevent permanent damage to a body structure. An elective procedure is not an SAE.

Important medical events that do not meet any of the criteria above may be considered serious when, based upon appropriate medical judgment, they may jeopardize the participant and may require medical or surgical intervention to prevent one of the outcomes listed in this definition. Examples of such medical events include allergic bronchospasm requiring intensive treatment in an emergency room or at home, blood dyscrasias or convulsions that do not result in inpatient hospitalization, or the development of drug dependency or drug abuse.

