9.0 STUDY TIME SCHEDULE

Study evaluation measures will be obtained over a 1-year period and will consist of seven scheduled assessments, not including screening and enrollment (Figure 1). Assessment visits will occur at baseline, 4 weeks, 8 weeks, 12 weeks, 6 months, 9 months and 12 months following randomization. The short-term follow-up visits will occur up to and including 12 weeks with the assessment of the primary outcome at 8 weeks, followed by long-term study visits at 6, 9 and 12 months. The following outlines the evaluations to be completed at each of the visits.

Figure 1. Study Time Schedule

Time Point	STUDY PERIOD								Early Termination Visit (ET)
	Screening/ Randomization - t1 (Visit 1)	Baseline t0 (Visit 2)	Short-term visits			Long-term follow-up			
			Week 4 (Visit 3)	Week 8 (Visit 4)	Week 12 (Visit 5)	Month 6 (Visit 6)	Month 9 (Visit 7)	Month 12 (Visit 8)	
ENROLLMENT									
Informed consent	x								
Eligibility screening	x								
Randomization	x								
Eligibility baseline		x							
INTERVENTIONS									
GeneSight Psychotropic (GEN)			_____	_____	_____	_____	_____	_____	
Enhanced GeneSight Psychotropic (E-GEN)			_____	_____	_____	_____	_____	_____	
Treatment as usual (TAU)			_____	_____	_____	_____	_____	_____	
ASSESSMENTS									
Buccal swab for genotyping	x								
Vital signs	x								
Mini International Neuropsychiatric Interview (MINI) for Axis 1	x								
Diagnostic and Statistical Manual of Mental Disorders, Fourth Edition, Text Revision (DSM-IV-TR) criteria for MDD	x								
DSM-IV-TR criteria for current substance use disorder	x								
Phlebotomy for laboratory panel	x								
Biobank sample	x								
Urine sample for drug screen and laboratory panel	x								
16-item Clinician Quick Inventory of Depressive Symptomatology (QIDS-C ₁₆)	x								
16-item Self Report Quick Inventory of Depressive Symptomatology (QIDS-SR ₁₆)	x	x	x	x	x			x	x
Changes to initial prescribing based on availability of pharmacogenomic data	x	x							
Medical history and psychiatric history	x	x							
Psychotropic medication history (current and past) and response	x	x							
Past (within one month) concomitant non-psychotropic medications	x	x							
Current concomitant non-psychotropic medications	x	x	x	x	x	x	x	x	x
Demographics, Employment, Insurance		x							
Smoking status and amounts		x	x	x	x			x	x
Height		x							
Weight and waist-to-hip ratio		x	x	x	x			x	x
Adverse events (AEs)		x	x	x	x			x	x

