9.6 Week 12 Visit (Visit 5)

Participants will return to the study center at the end of Week 12 \pm 4 days (Visit 5) of the study. In addition to the evaluations conducted at Week 8, the following will also be assessed:

- Psychiatric or quality of life evaluations:
 - CGI-S (Treating clinician)
 - CGI-I (Treating clinician)
 - CGI-EI (Treating clinician)
 - EQ-5D-5L
 - SF-36
 - Morisky scale (med compliance)
 - BARS scale (med compliance)

9.7 Long-Term Follow-Up - Months 6, 9 and 12 Visits (Visits 6, 7 and 8)

The long-term follow-up visits at the end of months 6 and 9 \pm 14 days (Visits 6 and 7) will be completed by telephone. The following will be evaluated at these visits:

- Psychiatric or quality of life evaluations:
 - HAM-D₁₇

- EQ-5D-5L
- SF-36 (only at month 6)
- Morisky scale (med compliance)
- BARS scale (med compliance)
- Current psychotropic medication and psychotropic medication trials since last visit
- Current concomitant non-psychotropic medications (including nicotine replacement and smoking cessation medications)
- Health resource utilization and productivity losses
- Documentation of disclosure of GEN report to participant at month 12 visit
- Participants will return to the study center at the end of month 12 (Visit 8) \pm 21 days of the study. The following will be evaluated at this visit:
- Psychiatric or quality of life evaluations:
 - QIDS-SR₁₆
 - HAM-D₁₇ (Central rater)
 - CGI-S (Treating clinician)
 - CGI-I (Treating clinician)
 - CGI-EI (Treating clinician)
 - PHQ-9
 - GAD-7
 - EQ-5D-5L
 - SF-36
- Smoking status and amounts
- Weight and waist-to-hip ratio
- Current psychotropic medication and psychotropic medication trials since last visit
- Current concomitant non-psychotropic medications (including nicotine replacement and smoking cessation medications)
- UKU side effect rating scale
- FIBSER
- AEs

- Medication adjustments (including dose changes, switching, augmentation and discontinuation)
- Medication compliance
- Health resource utilization and productivity losses

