### **2.1.4 Exploratory, Safety, and Tolerability Objectives**

- Mean percentage change in Generalized Anxiety Disorder 7-item (GAD-7) scale from baseline to end of Week 8, Week 12, Month 6, Month 9, Month 12;
- Percentage of responders and remitters at Week 8, Week 12, Month 6, Month 9, Month 12 on GAD-7 (see definition in 7.1 and 7.2);
- Change in SF-36 from baseline to end of Week 12, Month 6, Month 9, and Month 12;
- Percentage of responders at Week 12, Month 6, and Month 12 on SF-36 (see definition in 7.1);
- Mean percentage change in the Clinical Global Impression: Severity of Illness (CGI-S) from baseline to end of Week 12 and Month 12;
- Percentage of responders and remitters at Week 12 and Month 12 on CGI-S in each treatment group (see definition in 7.1 and 7.2);

- Percentage responders at Week 12 and Month 12 on CGI-I (Clinical Global Impression: Global Improvement) in each treatment group (see definition in 7.1);
- Percentage responders at Week 12 and Month 12 on CGI-IE (Clinical Global Impression: Efficacy Index) in each treatment group (see definition in 7.1);
- Compare congruence of medications between treatment groups at Week 8, Week 12, Month 6, Month 9, and Month 12 (see 7.5 for definition);
- Percentage of subjects who experienced adverse events (AE) at Week 8, Week 12, and Month 12;
- Change in Udvalg for Kliniske Undersogeler (UKU) side effect rating scale; Frequency, Intensity and Burden of Side Effects Ratings (FIBSER); and weight gain from baseline to Week 8, Week 12, and Month 12;
- Percentage of patients compliant with medications at Week 8, Week 12, Month 6, Month 9, and Month 12 between treatment groups using Brief Adherence Rating Scale (BARS) and prescription filling data

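### AEs are to be recorded at each visit, but the Month 6 and Month 9 telephone visits schedule no AE item, leaving about 40 weeks without a scheduled AE question

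*Protocol*

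**What the plan says.** Protocol section 17.2.2 sets the general rule: "At each visit all AEs that are observed, elicited by the Investigator, or reported by the participant, will be recorded". It makes no exception for telephone contacts. For each AE it requires at least the type, start and end dates, severity, seriousness, causality, action taken and outcome.

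Section 9.0 gives the schedule: "Assessment visits will occur at baseline, 4 weeks, 8 weeks, 12 weeks, 6 months, 9 months and 12 months following randomization". That is seven assessments. Section 9.7 numbers Months 6 and 9 as Visits 6 and 7 and says that they "will be completed by telephone. The following will be evaluated at these visits". The list that follows holds HAM-D17, EQ-5D-5L, SF-36 (Month 6 only), the Morisky and BARS adherence scales, psychotropic and concomitant medication, and resource use with productivity losses. AEs are not on it.

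Figure 1 agrees with section 9.7. Its AE row is marked at baseline, Weeks 4, 8 and 12, Month 12 and the ET visit, and is blank at Months 6 and 9. UKU, FIBSER and weight are blank there too.

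SAP section 2.1.4 plans to report "Percentage of subjects who experienced adverse events (AE) at Week 8, Week 12, and Month 12". SAP section 1.2 replaces the protocol's analysis plan. It does not address what is collected at each visit.

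**The concern.** The protocol contradicts itself about the two calls. A site that follows the section 9.7 list does not ask about AEs. A site that reads section 17.2.2 literally may do so. Long-term AE counts could then depend partly on how each site resolves the conflict.

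If the schedule is followed as written, AEs in the last three quarters of follow-up rest mainly on what participants recall at Month 12. Medication can be changed at any time (section 7.2), and both calls record psychotropic medication tried since the last visit, but neither asks how it was tolerated. Medication side effects, including weight gain, are a secondary objective (section 4.3). The Trial Monitoring Committee is to review accumulating safety data (section 2.4.3), and for this period it would have no scheduled AE data until Month 12, apart from ET visits.

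**Working it through.** The documents state no length for the gap, so there is no figure of theirs to reproduce. The check compares the visit lists and then does calendar arithmetic.

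**Where AEs are scheduled**

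| Assessment | AE item in Figure 1 and sections 9.3 to 9.7 |
|---|---|
| Baseline | yes |
| Week 4 | yes |
| Week 8 | yes (same evaluations as Week 4, section 9.5) |
| Week 12 | yes (section 9.6: "In addition to the evaluations conducted at Week 8, the following will also be assessed") |
| Month 6 (telephone) | no |
| Month 9 (telephone) | no |
| Month 12 | yes |

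The count is 5 of 7. The text and the figure agree visit by visit, so the omission is not an effect of a damaged table.

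**Length of the gap**

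Inputs: Week 12 is day 84, with a window of ±4 days (section 9.6). Month 12 has a window of ±21 days (section 9.7). The protocol does not define a month in days, so Month 12 is taken as 52 weeks (364 days), with 365 days as a check. Both visits are counted from the same starting point.

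- Nominal gap: 364 − 84 = 280 days; 280 / 7 = 40.0 weeks.
- With 365 days: 281 / 7 = 40.1 weeks.
- Windows combined: 4 + 21 = 25 days either way.
- Shortest: (280 − 25) / 7 = 36.4 weeks. Longest: (280 + 25) / 7 = 43.6 weeks. With 365 days these become 36.6 and 43.7.
- Share of follow-up: 40 / 52 = 77%.

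With 30-day months the nominal gap is (360 − 84) / 7 = 39.4 weeks, so the definition of a month changes little.

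**With an AE question at both calls**

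Taking Month 6 as week 26 and Month 9 as week 39:

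- Week 12 to Month 6: 26 − 12 = 14 weeks.
- Month 6 to Month 9: 39 − 26 = 13 weeks.
- Month 9 to Month 12: 52 − 39 = 13 weeks.

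Coverage becomes 7 of 7, and the longest nominal interval falls from about 40 weeks to about 14.

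**What already covers part of the gap**

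- *Volunteered events.* An AE mentioned on a call falls under section 17.2.2 and can be recorded. This depends on the participant raising it.
- *Early Termination visit.* Section 9.8 applies the Week 12 procedures, which include AEs, and section 14.1.2 asks for all efforts to bring withdrawn participants in. Those lost without this visit are not covered.
- *Resource use.* Both calls collect it, and section 8.2.3 includes hospital and emergency department use. It can signal a serious event. It does not supply the AE dates, severity, causality and outcome that section 17.2.2 requires, and no step transfers such an event to the AE CRF.

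**The case against.** The strongest reply is that the reduced set at the calls looks deliberate. Figure 1, section 9.7 and the SAP time points all fit together, and UKU and FIBSER are left out of the calls as well. On this view the only fault is one general sentence in section 17.2.2. That sentence can also be read as a rule for recording what comes to light, not as a demand for a scripted question; the screening visit carries no AE mark either. This has force. It shows that rewording section 17.2.2 would remove the contradiction. It would not shorten the gap.

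The reply also limits the consequences. A reader might infer any of the following, and the documents support none of them:

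- *Anyone who leaves after Week 12 contributes no further AEs.* The ET visit collects them. The statement fits only participants who also miss that visit and volunteer nothing.
- *Serious events would go undetected.* Hospital and emergency use is asked about at both calls, linked administrative data exist for consenting participants (section 8.2.3), HAM-D17 with its suicide item is given on the calls, participants may be seen clinically at any time (section 9.9), and the SAE reporting text in section 17.2.2 is not tied to a scheduled visit. Late discovery of some events is possible; wholesale loss is not shown.
- *The comparison between arms is biased.* The schedule is the same in all three arms, and nothing in the documents shows differential loss or differential asking.
- *The main result is affected.* The primary endpoint is at Week 8, before the gap begins.

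The AE percentages also sit under exploratory, safety and tolerability objectives, and SAP section 5.3 plans descriptive counts with modelling only as an option.

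**Conclusion.** The point holds as an inconsistency with a practical consequence for long-term safety data. AEs are scheduled at 5 of 7 assessments, and no AE question is scheduled for about 40 weeks (about 36 to 44 with visit windows), or about 77% of a 52-week follow-up. The Month 12 AE percentages may be under-counted and some serious events may be found late. The documents give no basis for stating how large the under-count would be.

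This rests on two assumptions: that Month 12 is 52 weeks or 365 days, and that sites follow the section 9.7 list as written. It is a low-cost improvement to the safety follow-up and does not challenge the trial's efficacy conclusion.

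**What to change.** Bring sections 17.2.2 and 9.7 and Figure 1 into agreement:

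1. Add an AE/SAE question covering the time since the last visit to the Month 6 and Month 9 call scripts, to the section 9.7 list and to the AE row of Figure 1.
2. State that any event revealed by the resource-use answers that qualifies as an AE or SAE is entered on the AE CRF with the fields that section 17.2.2 requires.

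Changing only the wording of section 17.2.2 would make the documents consistent but would leave the 40-week interval in place.

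The calls already take place, so the cost is a few minutes per call plus protocol and eCRF wording. Sample size, visit number and the Week 8 analysis do not change.
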